3.3.1.2 MAJOR ACUTE ADVERSE HEALTH EVENTS

A composite of any major adverse event over 12 months of follow-up, which includes: opioid overdose, other drug overdose, suicide attempt or other self-harm, hospitalizations (opioid and non-opioid), or death (from secondary data sources).

Rationale: This outcome assesses whether improved depressive symptoms and OUD and pain management has patient safety benefits.

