3.2 MAIN OUTCOMES

Outcomes are evaluated in the total population-based cohort of primary care patients randomized for the trial based on documented depression symptoms and evidence of an OUD in the prior year in electronic data sources. All outcome measures are obtained from secondary health services information that can be obtained for the entire study cohort (e.g., EHR, claims, health information exchanges and State prescription monitoring programs). No primary data will be directly collected from participants for outcomes because 50% of patients are never contacted by the study.

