3.3.1.3 SERIOUS OPIOID-RELATED EVENT

This is a count measure of the number of serious opioid-related emergency department (ED) visits or hospitalizations defined as any ED or hospital admission with a primary OUD or opioid-related diagnosis or an opioid-related overdose (lethal or non-lethal).³

Rationale: This outcome assesses whether improved management of depression, OUD and pain decreases dangerous opioid-related outcomes.

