3.3.1.4 OTHER SECONDARY EXPLORATORY OUTCOMES

Due to the heterogeneity of the sample and the expected heterogeneity of benefits across different subsamples (e.g., heroin use vs prescribed opioids for pain as route to OUD), a number of secondary outcomes will be used to describe outcomes. Each individual component of secondary outcomes (e.g., buprenorphine for pain, suicide attempt, opioid overdose) will also be evaluated independently.

- Descriptive measures related to OUD will be assessed in both arms, including engagement in primary care for OUD and/or pain; other treatments for OUD (e.g., naltrexone, methadone from outpatient treatment programs (OTPs) as well as behavioral treatments inside or outside the health system such as counseling for SUD or addiction treatment programs, or inpatient addiction treatment), secondary prevention outcomes (e.g., urine drug screening including fentanyl, naloxone prescription for OD prevention, Hepatitis C virus (HCV) and HIV screening, absence of non-buprenorphine opioid and benzodiazepine prescribing); chances in treatment for OUD (e.g., initiation of new buprenorphine for OUD); days of buprenorphine pain treatment (e.g., Belbuca, Butrans, etc.); and other treatments for pain (e.g., specialty treatments for pain, other pain treatments, and new buprenorphine for pain).
- Depression measures assessed during follow-up (both arms) will include measures of
 measurement-based care, medication treatment, and counseling or behavioral treatments for
 depression of other mental health disorders (e.g., no follow-up PHQ score documented in the
 EHR; number of documented PHQs in follow-up, new or change in antidepressant medication or
 increase in antidepressant dose in 12 months follow-up; counseling for depression, inpatient
 psychiatric treatment, and suicidal thoughts on PHQ-9).
- Risk factors for adverse or improved outcomes will include urine drug screens with "unexpected" outcomes (e.g., lack of prescribed buprenorphine, opioids not prescribed, methamphetamine and other drugs, cannabis); prescribed opioids aside from buprenorphine; chronic prescription opioids at doses exceeding CDC established safety threshold of ≥ 50 morphine milligram equivalents per day (MED); prescription opioid use above lowest level safety threshold (≥ 20 MED)^{34, 35}; prescribed benzodiazepines.

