10.3 ADVERSE EVENTS (AE) / SERIOUS ADVERSE EVENTS (SAE) AND REPORTING

We aim for harm reports to rely on data sources collected uniformly across study arms and not to include AEs and SAEs observed differentially among patients in the intervention arm. Many events, such as suicide, overdose, hospitalization and/or death may be documented in patients' electronic medical records (EMR) by NCMs (e.g., learned due to NCM outreach after missed appointments). Due to the pragmatic study design, such SAEs will not be observed in the control arm and use of EMR data may introduce bias. We therefore restrict harm monitoring to adverse events that lead to acute care in emergency departments or hospitalization, documentation of which are less likely to be biased by the intervention.

We will report self-harm (e.g., suicide attempt) and opioid or other drug overdose(s), that result in ED visits or hospitalizations (psychiatric and non-psychiatric), and all-cause mortality (by manner of death), in the intervention arm compared to usual care arms. We will include any intentional poisoning (overdose) as a suicide attempt as well. We will report the number, percent, and rate of these serious adverse events (SAEs) in each harm report for the DSMB to review. Formal sequential tests to compare SAEs between arms will not be conducted because the number and rate of events are expected to be too small to be able to detect statistically significant differences. Blinding will be in place to assure that the study team is not looking at outcome data across treatment arms during the trial.

There is a lag between when an event may occur and when the event information is recorded and available in the data sources utilized. To allow sufficient time for data capture, datasets used to generate the DSMB harm reports will be administratively censored according to a plan documented in an approved DSMB report template (up to a 3-month lag). We will be evaluating trial outcomes using a 6-month lag to allow us to maximal time to obtain completed claims and state death records (the latter of which have variable and unpredictable lags up to 24 months in Washington).

10.3.1 REPORTING OF INTERVENTION GROUP DEATHS AND UNEXPECTED AND RELATED SAES LEARNED OF INCIDENTALLY BY NCM

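### The major-adverse-event composite counts overdose and self-harm without the ED/hospital condition that 10.3 adopts because nurse-documented events would not be seen in usual care

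*Protocol*

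**What the plan says.** - **Composite (Protocol 3.3.1.2).** The outcome is any major adverse event over 12 months, "which includes: opioid overdose, other drug overdose, suicide attempt or other self-harm, hospitalizations (opioid and non-opioid), or death (from secondary data sources". No care setting is required for overdose or self-harm. The stated purpose is to see whether better management brings patient safety benefits.
- **Sources (3.2).** All outcomes come from "secondary health services information that can be obtained for the entire study cohort (e.g., EHR, claims, health information exchanges and State prescription monitoring programs". The EHR is named, and NCM entries are not excluded.
- **Harm monitoring (10.3).** After saying that NCMs may record suicide, overdose, hospitalization or death in the medical record, the protocol states that "such SAEs will not be observed in the control arm and use of EMR data may introduce bias". It continues: "We therefore restrict harm monitoring to adverse events that lead to acute care in emergency departments or hospitalization". Mortality is reported as "all-cause mortality (by manner of death", with no acute-care condition.
- **Neighbouring outcome (3.3.1.3).** The serious opioid-related event is a count "defined as any ED or hospital admission with a primary OUD or opioid-related diagnosis" or an opioid-related overdose, framed as ED visits or hospitalizations.
- **Components (3.3.1.4).** Each component of the secondary outcomes is also evaluated on its own; the examples given are "buprenorphine for pain, suicide attempt, opioid overdose".
- **Analysis (8.3.3).** The composite is compared between arms as time to first event, with Kaplan-Meier curves and a Cox model stratified by health system.

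**The concern.** The protocol identifies an ascertainment bias that depends on the arm, adopts a remedy for the safety reports, and then leaves the remedy out of an outcome that compares the arms on the same kinds of event. The reason given in 10.3 is that documentation differs by arm. That reason applies at least as strongly to a between-arm hazard ratio as to a monitoring table.

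The route by which an event could enter is plausible:

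- Under 10.1, NCMs hear of overdoses and suicide attempts, either incidentally or in structured assessments, and notify the primary care team.
- Under 6.4.2.5, they communicate mainly through the EHR.
- Under 6.1.3, usual care has no study contact at all.

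An overdose or self-harm event that never reached an ED could therefore be coded in the intervention arm and stay invisible in the control arm. The error would run in one direction, toward apparent harm or a masked benefit.

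**Working it through.** The protocol states no event rate, power or sample size for this composite, so there is no figure of its own to reproduce. The calculation below only illustrates the possible size.

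**Which events are exposed.** All hospitalizations count already, and ED-treated events meet the 10.3 condition. What remains is an overdose or self-harm event with no acute care, learned through the NCM and then coded in the EHR.

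**Inputs from the protocol.** There are 800 patients randomized 1:1, so 400 per arm (8.1 and 6.1.2). Engagement e is 30–50% (Table 8.1.1).

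**Inputs that are assumptions.**
- d, the share of engaged patients with such an NCM-only coded event: 0.5–1%.
- p, the 12-month risk: 20–50% for the composite, 2–3% for a single component.
- q, the chance that an affected patient has another composite event anyway: from p (independence) up to 80%.
- s, the share of the extra events that fall in the component examined: one third to all.

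**Extra patients counted in the intervention arm.** k = 400 × e × d.
- Lowest: 400 × 0.30 × 0.005 = 0.6.
- Highest: 400 × 0.50 × 0.01 = 2.0.
- As a share of the arm: 0.15% to 0.5%.

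**Composite, no true effect.** RR = 1 + k(1 − q)/(400p).
- p = 0.20, q = 0.20, k = 2.0: 1 + 1.6/80 = 1.020.
- p = 0.50, q = 0.50, k = 2.0: 1 + 1.0/200 = 1.005.
- p = 0.50, q = 0.80, k = 0.6: 1 + 0.12/200 = 1.0006.

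**Single component, no true effect.** RR = 1 + sk/(400p).
- p = 0.03, s = 1/3, k = 0.6: 1 + 0.2/12 = 1.017.
- p = 0.03, s = 1, k = 2.0: 1 + 2/12 = 1.167.
- p = 0.02, s = 1, k = 2.0: 1 + 2/8 = 1.25.

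**Against sampling error.** SE(log RR) = √(1/a + 1/b − 2/400), where a and b are the events per arm.
- With 8 and 10 events, SE = √0.22 = 0.469 and the 95% CI factor is exp(1.96 × 0.469) = 2.51.
- Over the component scenarios the factor runs from 2.14 to 2.62, so a spurious 1.25 would lie well inside the interval.

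**A much higher assumed rate.** Let x be the share of engaged, otherwise event-free patients with an NCM-only event, set at 2–10%. Then p1 = p0 + e·x·(1 − p0).
- Composite, p0 = 20–40%: HR = ln(1 − p1)/ln(1 − p0) runs from 1.01 to 1.23. The two-sided rejection rate at a nominal 5% runs from 5.1% to 27.7%.
- Single component, p0 = 3–6%: RR runs from 1.09 to 2.62.
- The top component case (p0 = 3%, e = 50%, x = 10%) needs 400 × 0.5 × 0.10 × 0.97 = 19.4 NCM-only events, against 400 × 0.03 = 12 events of that type from all other routes.

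**The case against.** The case for leaving the text alone has four parts.

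- **Section 10.3 governs harm monitoring only.** This is right. A reader might infer that the composite breaches 10.3, but the documents do not support that: the restriction is worded for harm monitoring. The point is that the stated reason was not carried over. Section 3.3.1.3 is only a limited comparator, because it is by design a count of acute visits and nothing says it was framed that way to avoid NCM bias.
- **The sources are mostly independent of the NCM.** Much of this stands. The missing-data section assigns Indiana health information exchange data to the adverse-outcome measures and describes automated records plus claims at KPWA. Section 13.3 has programmers extracting the records with coded programs, and 10.3 says: "We will be evaluating trial outcomes using a 6-month lag", to allow for completed claims and state death records. A reader might infer that free-text nurse notes feed the outcome; no section says so. Equally, no section makes exchange and claims data the only sources.
- **Codes and settings belong in the SAP.** Code lists do. Whether acute care is required is part of what the outcome is, and the protocol settles it for 3.3.1.3 and for harm monitoring.
- **The ED/hospital version is not arm-neutral either.** This is true, since NCMs triage patients to services. Section 10.3 claims only that such documentation is less likely to be biased, which is still an improvement.

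A reader might also extend the point to death. The 10.3 restriction gives no ground for that, because all-cause mortality is reported there without an acute-care condition.

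**Conclusion.** The point holds as a design choice worth correcting, at low severity. An ascertainment safeguard that the protocol itself justifies is missing from an outcome, and from its overdose and self-harm components, to which the same reasoning applies. The direction, against the intervention, follows from the text. The size does not: detection rates, event risks and overlap are all assumed.

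Under the low rates the distortion is negligible for the composite (at most 1.02). For a single component it is at most 1.25, within sampling error. A reader might infer from the higher rates that the composite test is seriously inflated. Nothing in the documents supports NCM-only coded events in up to 10% of engaged, otherwise event-free patients, and at the extreme such events would outnumber all others of their type. The conclusion that the effect is small for the composite is likely but not demonstrated. It also depends on hospitalizations making up most composite events, which the protocol does not state.

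**What to change.** In 3.3.1.2, and for the overdose and self-harm components evaluated under 3.3.1.4, state that the main version counts opioid overdose, other drug overdose and self-harm only when identified from an ED visit or hospitalization in encounter, claims or health information exchange data. Keep all hospitalizations and all-cause death unchanged. Report overdose and self-harm events coded without acute care by adding them in a sensitivity analysis, using the same model.

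The cost is one or two sentences of definition and no new data collection. Events coded only in outpatient care leave the main version in both arms, so somewhat fewer events are counted; how many cannot be known from the protocol. The ED/hospital version should be described as less prone to bias by arm, not as free of it.

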3.3.1.3 SERIOUS OPIOID-RELATED EVENT

This is a count measure of the number of serious opioid-related emergency department (ED) visits or hospitalizations defined as any ED or hospital admission with a primary OUD or opioid-related diagnosis or an opioid-related overdose (lethal or non-lethal).³

Rationale: This outcome assesses whether improved management of depression, OUD and pain decreases dangerous opioid-related outcomes.

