3.2.1 PRIMARY TRIAL OUTCOME

AIM 1. Days of OUD medication treatment. A continuous measure of days of OUD treatment with buprenorphine in the 365 days after randomization.

Rationale: We use days of OUD treatment with buprenorphine as our main outcome to reflect both buprenorphine initiation and/or retention. Days of OUD medication treatment was recently selected and prioritized as the most important core outcome measure in a Core Outcome Set by a NIDA Clinical Trials Network Delphi process. We also include several secondary measures of OUD treatment. Although a consensus is emerging that days of OUD treatment is the optimal measure for OUD

treatment, these secondary measures will provide a fuller picture of treatment in our sample: days of any medication treatment for OUD, sustained buprenorphine treatment for OUD for 90 days, 30 buprenorphine treatment for OUD with 80% of days covered, and any OUD or other addiction treatment. We restrict to buprenorphine because it is the first line office-based treatment and therefore represents most office-based OUD treatment, and because injectable naltrexone and methadone treatment for OUD cannot be obtained consistently through the Health Information Exchange in Indiana.

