measurement-based care, recommendations made to primary care provider, buprenorphine treatment for OUD, buprenorphine for pain, behavioral activation, specialty addiction treatment, and change in depression treatment. Each will be evaluated in the full intervention sample and in subgroups based on demographic and clinical characteristics (e.g., prior buprenorphine treatment, serious mental illness, prescribed opioids at baseline).

- Adoption of the intervention by primary care providers. We will evaluate measures of adoption at the primary care provider or team level: (e.g., buprenorphine treatment for OUD, buprenorphine treatment for pain, and change in depressive treatment).
- Implementation fidelity will be evaluated at the level of the NCM and the site, and will include evidence of NCMs consistent use of the core components of CC interventions (as described in Section 6.4.1.) such as: use of measurement based care, communication and/or coordination with patients' primary care teams (and, as appropriate specialists providing care), recommendation of evidence-based care for OUD and depression, and associated mental health and substance use conditions; use of BA for OUD and depression, and associated mental health and substance use conditions and attention to patient-centered care (e.g., engagement, and attention to other patient-prioritized conditions and concerns as appropriate).

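### The serious opioid-related event count does not separate hospital stays for addiction treatment, which the protocol elsewhere counts as OUD treatment, from dangerous events

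*Protocol*

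**What the plan says.** Protocol Section 3.3.1.3 makes the outcome a count of emergency department visits and hospitalizations and defines what qualifies: "any ED or hospital admission with a primary OUD or opioid-related diagnosis", or an opioid overdose, whether fatal or not. The direction of benefit is fixed by the rationale: "This outcome assesses whether improved management of depression, OUD and pain decreases dangerous opioid-related outcomes". No planned, detoxification or addiction-treatment stay is set apart.

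Two other sections treat addiction care as treatment received. Section 3.3.1.4 places "counseling for SUD or addiction treatment programs, or inpatient addiction treatment" among the other treatments for OUD, assessed in both arms. Section 3.2.1 adds a secondary measure, "any OUD or other addiction treatment".

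On what the intervention does, the reach measures in Section 3.2.3.1 include "specialty addiction treatment, and change in depression treatment" among the core elements whose uptake is tracked. Section 6.4.2.8 has the nurse help patients reach services to which they have been referred and remain in them. Section 6.1.3 says that the study has no contact with usual-care patients.

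**The concern.** A hospital stay for addiction treatment with OUD as the principal diagnosis meets both definitions. It is treatment received under Section 3.3.1.4 and a dangerous event under Section 3.3.1.3. The word serious does not narrow the count, because the definition that follows takes in any such admission.

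This matters more here than in a descriptive cohort, because one randomized arm is offered help in reaching addiction treatment and the other is not. If treatment stays differ between arms for that reason, the count no longer measures only the safety benefit that its rationale names. A real reduction in dangerous events could be hidden, or an apparent one could be overstated.

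**Working it through.** **The protocol's own figures.** There are none to reproduce. No event rate, power or sample size is given for this outcome, and no rate of inpatient addiction treatment.

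**Can such stays reach the data?** Yes. Sections 6.2.1, 6.6.2 and 11.2.3 each mention patients who are in inpatient treatment. Section 13.1 captures external hospital and emergency use through insurance claims at Kaiser Permanente Washington and the Indiana health information exchange at Indiana University Health. A residential stay that is not recorded as a hospital admission would not enter the count.

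**Illustration.** All rates are assumptions, per patient-year:
- λ is the usual-care rate of true dangerous events: 0.05, 0.10 or 0.20.
- RR is the true rate ratio for those events: 0.80.
- a0 and a1 are treatment admissions in usual care and intervention.
- There are about 400 patients per arm, from the minimum of 800 in Section 8.1 randomized 1:1, each followed for a year.

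Observed ratio = (RR × λ + a1) / (λ + a0). With treatment admissions left out of the count, it is 0.80 throughout.

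| λ | a0 = a1 = 0.01 | a0 = 0.01, a1 = 0.03 | a0 = 0.03, a1 = 0.01 |
|---|---|---|---|
| 0.05 | 0.05/0.06 = 0.83 | 0.07/0.06 = 1.17 | 0.05/0.08 = 0.625 |
| 0.10 | 0.09/0.11 = 0.82 | 0.11/0.11 = 1.00 | 0.09/0.13 = 0.69 |
| 0.20 | 0.17/0.21 = 0.81 | 0.19/0.21 = 0.90 | 0.17/0.23 = 0.74 |

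Equal admissions dilute the effect slightly. An excess in the intervention arm hides or reverses it. A deficit exaggerates it.

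**Break-even.** The observed ratio is 1.00 when a1 − a0 = (1 − RR) × λ:
- λ = 0.05: 0.20 × 0.05 = 0.01, or 4 extra admissions per 400.
- λ = 0.10: 0.20 × 0.10 = 0.02, or 8 per 400.
- λ = 0.20: 0.20 × 0.20 = 0.04, or 16 per 400.

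**What that asks of engaged patients.** Table 8.1.1 considers 30-50% engagement, which is 120 to 200 of 400. If the excess arises only among them, 4 extra admissions is 4/200 to 4/120, or 2.0 to 3.3 per 100 engaged. Sixteen is 16/200 to 16/120, or 8.0 to 13.3 per 100.

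**The case against.** A reader might infer that nurses steer patients into inpatient treatment, so that the intervention arm's count must rise and the comparison is biased toward harm. Assumed figures can be made to show this: 2 extra treatment admissions on 20 events per 100 gives 22/20 = 1.10, and 5 on 10 gives 15/10 = 1.50, with no change in dangerous events. The documents do not support that reading:
- No section says that nurses promote inpatient admission. Section 6.4.2.6 has medication usually started at home. The referral examples in Section 6.4.2.8 are psychiatry, counseling and external methadone treatment.
- Sections 6.2.1 and 11.2.3 mention inpatient treatment as a reason to hold off or pause contact, not as a goal.
- Office-based buprenorphine could just as well reduce detoxification or withdrawal admissions.
- The 1.10-1.50 range leaves out no difference and any reduction.

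These points stand, and they leave the direction open.

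Three further objections carry part of their weight:
- **Components are read separately.** Section 3.3.1.4 promises this, so overdose can be seen alone. But a split between overdose and other OUD admissions still leaves treatment stays mixed with acute admissions, and the named count stays mixed. The board's harm reports (Section 10.3) use self-harm, overdose and mortality, so safety monitoring is unaffected.
- **This is detail for the analysis plan.** Code lists are. The definition itself is stated in the protocol, and Section 8.3.3 defers the analytic approach, not the meaning of the outcome. The definition carries a citation whose exclusions cannot be judged from the protocol, but the text as written has none.
- **An exclusion could remove real harm.** Dropping every detoxification stay might discard unplanned relapse or withdrawal admissions. The rule has to guard against that.

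**Conclusion.** The point holds as a misclassification in a stated outcome definition: the same hospital stay can be scored as treatment and as a dangerous event. Because linkage support is given in one arm only, the misclassification may differ by arm. Neither its direction nor its size can be determined from the protocol, and a claim of bias toward harm is not supported.

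The size is illustrative only. With 0.05 to 0.20 true events per patient-year and a true 20% reduction, 4 to 16 extra treatment admissions in about 400 intervention patients would bring the observed ratio to 1.00. Equal rates of 0.01 would give 0.81 to 0.83. Every rate is an assumption, and these are shifts in a point estimate.

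The outcome is secondary and unpowered, and the primary outcome is untouched. The change is still worth making, because it is cheap and the count is the protocol's named test of fewer dangerous opioid outcomes.

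**What to change.** Before unblinding, amend Section 3.3.1.3 to set one code rule, applied identically to both arms and both sites:
- Separate planned or addiction-treatment-program hospital admissions, with no overdose or acute opioid complication coded, from acute emergency visits and admissions.
- Use the acute events as the serious opioid-related event count.
- Report the treatment admissions separately by arm.
- Give the unrestricted count, as now defined, as a sensitivity analysis.

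The hospitalization part of the composite in Section 3.3.1.2 has the same overlap, so the wording there should be checked at the same time.

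The cost is outcome wording and code lists, with no new data collection. There are two small downsides. Facility or admission-type codes may differ between claims and health information exchange data, so some stays may be misclassified. The restricted count is also less comparable with the cited definition. Reporting the unrestricted count alongside covers both.
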